# Clinical Study Protocol

## Johnson & Johnson Vision Care, Inc.

will be used to model the residual errors between measurements within the same subject across time (R-side). The log-likelihood ratio test will be used to assess homogeneity between the residual covariance structure across ARM. The Kenward and Roger method will be used to calculate the denominator degree of freedom.

### **Hypothesis Testing:**

The null and alternative hypotheses for non-inferiority of the Test relative to Control are as follows:

$$H_0: \Delta \leq -5$$

$$H_A: \Delta > -5,$$

where  $\Delta$  is the difference between lens types (Test minus Control) in mean change from baseline at 2-week follow-up. Non-inferiority of the Test lens relative to the Control lens will be based on the LSM difference in the score change from baseline at 2-week follow-up and its corresponding 95% confidence interval from the final model. The lower bound of the 95% CI will be compared to the non-inferiority margin of -5. If the lower bound is greater than -5, the null hypothesis will be rejected, and the Test lens will be considered non-inferior to the Control lens. If non-inferiority of the Test lens over Control lens is met, then superiority test will be also conducted on the ITT population. If the lower bound is greater than 0, then the superiority of the Test lens over the Control lens will be established

### **14.6. Secondary Analysis**

The secondary endpoints are the change in (1) CLDEQ-8 total score from baseline to 2-week, (2) CLDEQ-8 total scores and (3) CLUE comfort scores at 2-week follow-up. For the first secondary endpoint, the data from the ARM 1 (Test) will be compared to the first period of the ARM 2 (Control, habitual lens). The analysis will be conducted on the Per-Protocol (PP) population. A sensitivity analysis will be conducted on the Intent-to-Treat (ITT) population. Non-inferiority will be assessed on PP population, while superiority will be assessed on ITT population. The remaining other secondary analyses will be conducted on the PP population within the ARM 2 only.

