#### **3.2. Inclusion Criteria**

Potential subjects must satisfy all of the following criteria to be enrolled in the study:

Inclusion Criteria after Screening:

1. The subject must read, understand, and sign the STATEMENT OF INFORMED CONSENT and receive a fully executed copy of the form.
2. Appear able and willing to adhere to the instructions set forth in this clinical protocol.
3. Between 18 and 59 (inclusive) years of age at the time of screening.
4. Be a daily disposable current soft contact lens wearer in both eyes with a minimum of 6 days/week wear time over the last 1 month by self-report.
5. Have a CLDEQ-8 score of 15 or greater with the habitual lens.
6. Subjects must possess a pair of spectacles for distance correction.

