**Clinical Study Protocol**  
**Johnson & Johnson Vision Care, Inc.**

| ARM 2  |                                |  |
|---|--------------------------------|--|
| Visit 2: Treatment 1, 2-Week Follow-Up; Treatment 2 Fitting |                                |  |
| Step  | Procedure                      | Details  |
| 2.5.  | CLDEQ-8 Questionnaire          | 
The subject will respond to the CLDEQ-8 Questionnaire (Appendix A).
 
NOTE: If subjects no longer meet score criteria of <math>\geq 15</math>, the lenses will be removed by the subject and discarded. The subject will be discontinued and proceed to final evaluation (F.1)
   |
| 2.6.  | Follow Up questionnaires       | 
The subject will respond to the CLUE and MRD Follow Up Questionnaire (Appendix A)
   |
| 2.7.  | Entrance Visual Acuity         | 
Record the distance Snellen visual acuity with the contact lenses (OD, OS) to the nearest letter. Subjects must read the smallest line until at least 50% of the letters are read incorrectly.
  |
| 2.8.  | Subjective Lens Fit Assessment | 
Evaluate overall lens fit acceptance (acceptable or unacceptable) based on centration, movement and other fitting characteristics.
 
An unacceptable fit is deemed by one of the following criteria:
 
 
• limbal exposure at primary gaze or with extreme eye movement.
 
• edge lift.
 
• excessive movement in primary and up gaze.
 
• insufficient movement in all three of the following conditions: primary gaze, up gaze, and Josephson push up.
 
 
NOTE: if lens fit is unacceptable subject will be discontinued from the study.
 |
| 2.9.  | Lens Removal and Discard       | 
The lenses will be removed by the subject and discarded.
  |

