Table 9 displays the sample size estimates for the primary endpoint of CLUE Comfort score, and the secondary endpoint of CLDEQ8- Scores for different scenarios of effect sizes. CLDEQ-8 power analysis was provided for informational purposes. All Sample size calculations were performed with 80% power and 2-sided alpha=0.05. With respect to CLDEQ-8 Scores, for ARM1 a standard deviation of 7.17 was utilized (See Table 7 ), while a standard deviation of 5.0 was utilized for ARM2 in each calculation for the various effect sizes. The different effect sizes for CLDEQ-8 scores were based on the historical effect sizes provided in Table 7. Historically, on average AO1D improved CLEQ8-scores about 7 points after 2-weeks of wear. The power analysis for CLDEQ8-scores is displayed in Table 9 below. With respect to CLUE comfort scores, for ARM1 a standard deviation of 25.21 was used (See Table 8) while, a standard deviation of 18.12 was utilized for ARM2 in the calculation for each scenario. Due to the varying effect sizes displayed in Table 8 above, effect sizes of 3, 5 and 9 were utilized as a more conservative estimate for the sample size calculation since there was a high a difference observed between AO1D and subjects' habitual lenses with respect to CLUE Comfort (22.6 points) in ██████.

Sample size and power calculations for each endpoint and scenario were calculated using a 2-sided Satterthwaite t-test assuming unequal variances using the POWER^11 procedure in SAS Version 9.4.

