#### **Per-Protocol Population:**

All subjects who successfully complete all visits and do not substantially deviate from the protocol as determined by the trial cohort review committee prior to database hard lock. Justification for the exclusion of subjects with protocol deviations from the per-protocol population set will be documented in a memo to file.

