### **CLDEQ-8 Total Scores:**

The CLDEQ-8 total scores will be analyzed using a linear mixed model to assess the difference between the Test and Control (subjects' habitual lens) lenses within ARM 2. The regression model will include lens type (Habitual lens and AO1D), and baseline score as fixed effect factors. Baseline characteristics such as age and gender may be included as fixed effect covariates in the model when appropriate Investigational site will be included as a random effect.. The correlation measurements from the same subjects across lens type (Habitual and AO1D) will be model using Unstructured (UN) variance-covariance matrix. If the estimation algorithm does not converge, then a Compound Symmetry (CS) or heterogenous compound symmetric (CSH) matrix will be used. The Kenward and Roger method will be used to calculate the denominator degree of freedom.

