### **Hypothesis Testing:**

The null and alternative hypotheses for non-inferiority of the Test relative to Control are as follows:

$$H_0: \Delta \geq 3$$

$$H_A: \Delta < 3,$$

where  $\Delta$  is the difference between lens types at 2-week follow-up (Test (AO1D) minus Control (Habitual Lenses)). Non-inferiority of the Test lens relative to the Control lens will be teste using a 2-sided 95% CI constructed for the LSM difference at 2-week follow-up Non-inferiority will be established if the upper bound of the 95% CI is below 3 CLDEQ-8 points. If non-inferiority of the Test lens over Control lens is met, then superiority test will be also conducted on the ITT population. If the upper bound is less than 0, then the superiority of the Test lens over the Control lens will be established.

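### The within-ARM 2 CLDEQ-8 non-inferiority test selects subjects on its own control score, so its 2.5% one-sided error generally does not hold; the size depends on a repeat-score correlation the documents do not give

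*Combined protocol and SAP*

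**What the plan says.** Four provisions act together.

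- **Entry (Section 3.2).** "Have a CLDEQ-8 score of 15 or greater with the habitual lens", measured at Visit 1.
- **ARM 2 Visit 2, Step 2.5 (Section 7.2).** The note opens "If subjects no longer meet score criteria of" 15 or more, and gives the consequence: "The subject will be discontinued and proceed to final evaluation (F.1", the final evaluation step. This happens before AO1D is fitted. Step 2.5 for ARM 1 carries no such note.
- **Per-protocol set (Section 14.3).** "All subjects who successfully complete all visits and do not substantially deviate from the protocol". In ARM 2 that requires Visit 3, and so a Visit 2 score of at least 15.
- **Within-ARM 2 test (Section 14.6).** "The remaining other secondary analyses will be conducted on the PP population within the ARM 2 only". The contrast is AO1D minus habitual lens at two weeks, and "Non-inferiority will be established if the upper bound of the 95% CI is below 3 CLDEQ-8 points". On the model: "The regression model will include lens type (Habitual lens and AO1D), and baseline score as fixed effect factors".

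ITT is used for the superiority step. Section 14.6 attaches its ITT sensitivity analysis to the first, between-arm secondary endpoint. Section 14.9 offers multiple imputation only as a sensitivity analysis when dropout exceeds 15%.

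**The concern.** The Visit 2 habitual-lens score does two jobs: it decides who stays in the analysis, and it is the value subtracted from the AO1D score. A subject who scored low on the habitual lens by chance is removed, while one who scored high by chance is kept and tends to score lower next time on any lens. The Visit 3 AO1D score faces no matching filter. The paired difference can therefore look better for AO1D than the true lens effect.

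The baseline covariate does not correct this. It is the same on both of a subject's records, so with complete pairs it drops out of the lens contrast. Replacing discontinued subjects (Section 8.2) refills ARM 2 with subjects who passed the same filter. The problem is separate from the fixed lens order and would remain with no period effect.

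At stake is a formal non-inferiority conclusion in a study that Section 2.1 says is meant to support market claims.

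**Working it through.** **The plan's own figures.** "All Sample size calculations were performed with 80% power and 2-sided alpha=0.05". A two-sided 95% interval used for non-inferiority has 2.5% one-sided error. Table 9 reproduces: for CLUE comfort at effect 9 the distance to the margin is 9 + 5 = 14. With SDs 25.21 and 18.12 and 40 per arm, SE = √((25.21² + 18.12²)/40) = 4.91. The Satterthwaite calculation returns 120, 77 and 40 per arm for effects 3, 5 and 9, as printed. The plan states no error rate for the within-ARM 2 test beyond the nominal interval.

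**Inputs.** n = 40 completers (Section 4.3), margin 3, cut at 15. Table 7 gives habitual 20.3 (SD 4.39), AO1D SD 6.35 and SD of the difference 7.17. Section 14.2 gives a habitual-change SD of 5.0. Table 7 implies r = (6.35² + 4.39² − 7.17²)/(2 × 6.35 × 4.39) = 0.15 between AO1D and habitual baseline. Neither a habitual repeat-score correlation nor a Visit 2 distribution is given; these are assumed below.

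**Direction.** Let β = r × SD(AO1D)/SD(habitual), and let L be the rise in the mean Visit 2 score caused by the cut. With a true difference of exactly +3, the expected difference among those kept is 3 − (1 − β)L. It favours AO1D when β is below 1, vanishes at β = 1, and reverses above 1.

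**Hand calculation, Table 7 values taken as the Visit 2 distribution.** Whole-number scores put the cut at 14.5.
- z = (14.5 − 20.3)/4.39 = −1.32, so about 9% are discontinued. L = 4.39 × 0.1667/0.9068 = 0.81.
- AO1D SD 6.35, r = 0.15: β = 0.22, bias = −0.78 × 0.81 = −0.63. SE = 7.17/√40 = 1.13. Pass rate ≈ Φ(0.63/1.13 − 2.02) = Φ(−1.46) ≈ 7%; simulation gives about 8%.
- AO1D SD 6.35, r = 0.7: β = 1.01, bias about 0, pass rate nominal.

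**Simulation.** Normal scores rounded to whole numbers, true difference +3 in all ARM 2 subjects, subjects below 15 at Visit 2 dropped, paired 95% interval, n = 40. In the first four rows the Visit 1 entry cut is modelled as well. The Table 7 fit has an underlying mean of 14.4 and SD of 7.3, giving 20.3 (4.39) among those at or above 15. A habitual correlation of 0.75 then gives a change SD of about 5.0.

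| Scenario | Discontinued at Step 2.5 | Bias | False-pass rate |
|---|---|---|---|
| Table 7 fit, equal SDs, all correlations 0.75 | 23% | −0.96 | 22% |
| Same, AO1D correlation 0.5 | 23% | −1.39 | 24% |
| Assumed mean 17, SD 6, equal SDs, correlation 0.61 | about 22% | about −1.0 | 21% (25% unrounded) |
| Table 7 fit, underlying AO1D SD 6.4, AO1D correlation 0.25 | 23% | −1.9 | 37% |
| Visit 2 mean 19.5, SD 4.39; AO1D SD 6.35, r 0.15 | 13% | −0.83 | 11% |
| Same, r 0.35 | 13% | −0.52 | 8% |
| Same, r 0.5 | 13% | −0.30 | 5% |
| Same, r 0.7 | 13% | about 0 | 2.5% |

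Check on the first row: SD of the difference = 7.31 × √(2 × 0.25) = 5.17, SE = 5.17/√40 = 0.82, and Φ(0.96/0.82 − 2.02) = Φ(−0.85) ≈ 20%, close to the simulated 22%. Dropping the Step 2.5 selection returns 2.1% to 2.9%.

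**The case against.** The strongest objection concerns size. The documents fix neither the repeat-score correlation nor the Visit 2 distribution. The larger rates need the AO1D score to be no more variable than the habitual score, or only weakly correlated with it. Table 7 shows a larger AO1D SD (6.35 against 4.39), and with a larger SD and a correlation near 0.7 the bias disappears. This stands. A reader might infer from the table that the error is several times nominal whatever the assumptions, or that the bias always favours AO1D. The documents support neither reading. Nor is 26% a ceiling: the 37% row comes close to Table 7's AO1D and difference SDs, but its low correlation is again an assumption for Visit 2 to Visit 3.

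Second, the plan has partial safeguards. ITT for superiority and multiple imputation do retain discontinued subjects, and Section 14.1 defers detail to a stand-alone SAP. None of these changes the non-inferiority decision. If Step 2.5 removed 23% of ARM 2 alone, dropout across two equal arms would be about 12%, so the 15% trigger might not be reached.

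Third, the consequence is limited. Section 2.3 requires the primary to be met first. A reader might infer that passing this test alone opens the within-ARM 2 CLDEQ-8 item tests. It does not: Sections 2.3 and 14.4 require both CLDEQ-8 secondaries, and Section 14.7 requires all primary and secondary hypotheses.

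**Conclusion.** The plan is wrong as written. The non-inferiority test conditions on its own control value, and no provision corrects that decision. The direction generally favours AO1D.

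The size is conditional. For a lens exactly at the margin, about 40 completers and this test alone:
- about 20% to 26% with the population matched to Table 7 or to an assumed mean 17, SD 6, habitual-change SD about 5.0, and equal SDs;
- about 6% to 11% in most scenarios with a larger AO1D SD;
- near nominal with a larger AO1D SD and a correlation of about 0.7.

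The unconditional rate is lower because the primary must pass first. A reader might also carry these figures over to the within-ARM 2 CLUE comfort test. The documents give no correlation between CLUE comfort and CLDEQ-8, so no figure is offered for it.

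**What to change.** Replace the analysis set and model for this test in Section 14.6 with:

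> The within-ARM 2 CLDEQ-8 non-inferiority model will be fitted by REML to all ARM 2 subjects with a Visit 2 CLDEQ-8 score and no substantial deviation, including those discontinued at Step 2.5, whose Visit 2 score is retained. The model will include lens type, baseline score and lens type by baseline interaction, with an unstructured covariance; the lens contrast is evaluated at the mean baseline of all included ARM 2 subjects. If UN does not converge, CSH will be used. The PP-completer contrast is supportive only.

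Step 2.5 dropout depends only on a recorded score, so a likelihood analysis that keeps that score can allow for it. The interaction is needed. With the planned single baseline slope, a bias of −0.3 to +0.3 points remains when AO1D correlations differ from habitual ones; with a separate slope per lens the false-pass rate is 2.1% to 3.0%. CSH is a safe fallback because, with two lens conditions, it has the same two variances and one correlation as UN, whereas CS would force equal variances.

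The Step 2.5 rule itself is left as it is. The cost is SAP wording, before the SAP is finalised ahead of database lock, with no extra subjects, visits or data. The small downside is that the AO1D mean for discontinued subjects is model-based, so the interval is somewhat wider and the result less favourable to AO1D.

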### **Change in CLDEQ-8 Total Scores:**

The CLDEQ-8 total scores will be analyzed using a linear mixed model to assess the difference between the Test and Control (subjects' habitual lens) lenses. The regression model will include ARM (ARM1 – Test, and ARM 2 – Habitual Lens), time (Baseline and Follow-up evaluation) and ARM by time interaction as fixed effect factors. Baseline characteristics such as age and gender may be included as fixed effect covariates in the model when appropriate. Investigational site will be included as a random effect (G-side). An Unstructured (UN) or compound symmetric (CS) covariance or heterogenous compound symmetry (CSH) structures will be used to model the residual errors between measurements within the same subject across time (R-side). The log-likelihood ratio test will be used to assess homogeneity between the residual covariance structure across ARM. The Kenward and Roger method will be used to calculate the denominator degree of freedom.

# Clinical Study Protocol

## Johnson & Johnson Vision Care, Inc.

### **Hypothesis Testing:**

The null and alternative hypotheses for non-inferiority of the Test relative to Control are as follows:

$$H_0: \Delta \geq 3$$

$$H_A: \Delta < 3,$$

where  $\Delta$  is the difference between lens types (Test minus habitual lens) in mean change from baseline at 2-week follow-up. Non-inferiority of the Test lens relative to the Control lens will be based on the least square mean (LS Mean) difference in the score change from baseline at 2-week follow-up and its corresponding 95% confidence interval (CI) from the final model. The upper bound of the 95% CI will be compared to the non-inferiority margin of 3. If the upper bound is less than 3, the null hypothesis will be rejected, and the Test lens will be considered non-inferior to the Control lens. If non-inferiority of the Test lens over Control lens is met, then superiority test will be also conducted on the ITT population. If the upper bound is less than 0, then the superiority of the Test lens over the Control lens will be established.

### **CLDEQ-8 Total Scores:**

The CLDEQ-8 total scores will be analyzed using a linear mixed model to assess the difference between the Test and Control (subjects' habitual lens) lenses within ARM 2. The regression model will include lens type (Habitual lens and AO1D), and baseline score as fixed effect factors. Baseline characteristics such as age and gender may be included as fixed effect covariates in the model when appropriate Investigational site will be included as a random effect.. The correlation measurements from the same subjects across lens type (Habitual and AO1D) will be model using Unstructured (UN) variance-covariance matrix. If the estimation algorithm does not converge, then a Compound Symmetry (CS) or heterogenous compound symmetric (CSH) matrix will be used. The Kenward and Roger method will be used to calculate the denominator degree of freedom.

### **Hypothesis Testing:**

The null and alternative hypotheses for non-inferiority of the Test relative to Control are as follows:

$$H_0: \Delta \geq 3$$

$$H_A: \Delta < 3,$$

where  $\Delta$  is the difference between lens types at 2-week follow-up (Test (AO1D) minus Control (Habitual Lenses)). Non-inferiority of the Test lens relative to the Control lens will be teste using a 2-sided 95% CI constructed for the LSM difference at 2-week follow-up Non-inferiority will be established if the upper bound of the 95% CI is below 3 CLDEQ-8 points. If non-inferiority of the Test lens over Control lens is met, then superiority test will be also conducted on the ITT population. If the upper bound is less than 0, then the superiority of the Test lens over the Control lens will be established.

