### **2.3. Hypotheses**

Primary Hypothesis:

The Primary hypothesis will be evaluated between the two study arms; only the first period will be considered for the second study arm.

| Primary Hypotheses |   |
|--------------------|---|
| Endpoint           | Hypothesis  |
| CLUE Comfort       | The Test lens will be non-inferior to the Habitual lens with respect to the change in CLUE comfort score from baseline at 2-week follow-up. A non-inferiority margin of -5 points on the CLUE scale will be used. |

Secondary Hypotheses:

The primary hypothesis must be met in order to test the secondary hypotheses. The secondary hypothesis regarding the change in CLDEQ-8 Scores will be evaluated between the two study arms; only the first period will be considered for the second study arm. The remaining two secondary hypotheses will be evaluated within the second study arm only.

| Secondary Hypotheses          |  |
|-------------------------------|--|
| Endpoint                      | Hypothesis   |
| Change in CLDEQ-8 Total Score | The Test lens will be non-inferior to the Habitual lens with respect to the change in CLDEQ-8 total score from baseline at 2-week follow-up. A non-inferiority margin of 3 points on the CLDEQ-8 scale will be used. |
| CLDEQ-8 Total Score           | The Test lens will be non-inferior to the Habitual lens with respect to CLDEQ-8 total score at 2-week follow-up. A non-inferiority margin of 3 CLDEQ-8 points will be used.  |
| CLUE Comfort                  | The Test lens will be non-inferior to the Habitual lens with respect to CLUE comfort score at 2-week follow-up. A non-inferiority margin of -5 CLUE points will be used.   |

The primary hypothesis must be met in order to satisfy the objective of the study.

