## **4. STUDY DESIGN AND RATIONALE**

### **4.1. Description of Study Design**

This is a multi-site, randomized, bilateral, dispensing, parallel design study with two arms (ARM 1 and ARM 2). Subjects will be pre-screened for contact lens related dryness symptoms via phone or email prior to enter the study.

Subjects in ARM 1 will be fitted into AO1D and followed up after 2 weeks of wear. Subjects will be masked to the identity of the lens assigned. There will be 2 visits as follows:

- Pre-screen questions via. phone or email
- Visit 1: Screening, baseline evaluation, fitting AO1D
- Visit 2: 2-week follow up and final evaluation

Subjects in ARM 2 will be first fitted into their habitual lenses and dispensed for 2 weeks. At the follow-up visit, subject will be fitted into AO1D and followed up after 2 weeks of where. Subjects will not be masked to their habitual lens (open label), but they will be masked to the identity of AO1D during the second period of wear. There will be 3 visits as follows:

- Pre-screen questions via phone or email
- Visit 1: Screening, baseline evaluation, fitting habitual lens
- Visit 2: 2-week habitual lens follow up; fitting AO1D
- Visit 3: 2-week AO1D follow up and final evaluation

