## **5. TEST ARTICLE ALLOCATION AND MASKING**

### **5.1. Test Article Allocation**

This will be a randomized 2-arm study. This study is parallel design with 2 arms such that the first arm (refer as "ARM 1") is designed with 1 lens (the AO1D) while the second arm (refer as "ARM 2") is designed with 2 lenses wearing (habitual lens and AO1D) respectively. Subjects in the ARM 1 will receive the AO1D in a bilateral fashion for approximately 2 weeks, while the subjects in ARM 2 will first receive the open labeled habitual lens to wear bilaterally for approximately 2 weeks during the first wear period and then receive the AO1D to wear bilaterally for approximately 2 weeks during the second wear period.

Subjects will be randomly assigned to either ARM 1 or ARM 2 based on a computer-generated randomization schedule prepared before the study initiation. The randomization scheme will be generated using the PROC PLAN procedure from Statistical Analysis System (SAS) Software Version 9.4 or higher (SAS Institute, Cary, NC) provided by the study biostatistician.

The study site must follow the randomization scheme provided and complete enrollment per the randomization list and not pre-select or assign subjects. The randomized assignment of subjects will be performed at the first visit prior to the first fitting. The following must have occurred prior to randomization:

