**Clinical Study Protocol**  
**Johnson & Johnson Vision Care, Inc.**

| Visit 1: Baseline & Randomization |                                |   |     |
|-----------------------------------|--------------------------------|---|-----|
| Step                              | Procedure                      | Details   |     |
| 1.16                              | Randomization                  | Eligible subjects will be randomized to either ARM 1 (single arm) or ARM 2 (crossover), based on the randomization scheme.  | N/A |
| 1.17                              | Lens Selection                 | Select the contact lens power based on subjective best sphere refraction.   | N/A |
| 1.18                              | Lens Insertion                 | The subject will insert the study lenses. Record the time of lens insertion. Check for lens damage under the slit lamp before proceeding with lens settling. Replace damaged lenses if applicable.  | N/A |
| 1.19                              | Lens Settling                  | Allow the study lenses to settle for a minimum of 5 minutes.  | N/A |
| 1.20                              | Subjective Lens Fit Assessment | 
Evaluate overall lens fit acceptance (acceptable or unacceptable) based on centration, movement and other fitting characteristics.
 
An unacceptable fit is deemed by one of the following criteria:
 
 
• limbal exposure at primary gaze or with extreme eye movement.
 
• edge lift.
 
• excessive movement in primary and up gaze.
 
• insufficient movement in all three of the following conditions: primary gaze, up gaze, and Josephson push up.
 
 
NOTE: if lens fit is unacceptable subject will be discontinued from the study.
 |     |

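### In ARM 2 AO1D is always worn second, so the two within-ARM 2 secondary contrasts measure lens plus period and cannot by themselves establish non-inferiority or superiority of the lens

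*Combined protocol and SAP*

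**What the plan says.** Section 4.1 fixes the order in ARM 2: "Subjects in ARM 2 will be first fitted into their habitual lenses and dispensed for 2 weeks", then "Visit 2: 2-week habitual lens follow up; fitting AO1D", then "Visit 3: 2-week AO1D follow up and final evaluation". No group wears the lenses in the reverse order. Section 5.1 randomises the arm only: "Subjects will be randomly assigned to either ARM 1 or ARM 2 based on a computer-generated randomization schedule prepared before the study initiation". Step 1.16 in Section 7.2 nevertheless labels ARM 2 a crossover: "Eligible subjects will be randomized to either ARM 1 (single arm) or ARM 2 (crossover)".

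Section 2.3 places the CLDEQ-8 total score and CLUE comfort hypotheses inside that arm: "The remaining two secondary hypotheses will be evaluated within the second study arm only". For CLDEQ-8, Section 14.6 says "The regression model will include lens type (Habitual lens and AO1D), and baseline score as fixed effect factors"; age and gender are optional and site is random. The CLUE model has the same structure. Neither has a period term.

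The decision rules are stated about the lens. For CLDEQ-8, an upper 95% limit below 3 gives non-inferiority, and then "If the upper bound is less than 0, then the superiority of the Test lens over the Control lens will be established". The CLUE rule mirrors this with a margin of -5 and a lower limit above 0. Non-inferiority is judged on the Per-Protocol set and superiority on ITT.

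Step 2.5 of the ARM 2 Visit 2 procedures discontinues subjects whose CLDEQ-8 no longer reaches 15, before AO1D is fitted. ARM 1 has no such rule at its Visit 2.

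The plan states no assumption of zero period effect and no limitation on this point.

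**The concern.** A crossover separates lens from period by having both orders. ARM 2 has one, so anything that moves scores between Visit 2 and Visit 3 for a reason other than the lens is credited to AO1D. Section 2.1 says the study is meant mainly to support market claims. The two contrasts carry two of the three secondary hypotheses, and Section 14.4 lets them open the within-ARM 2 tertiary items, which have the same single order. The preference questions, asked only at Visit 3 of ARM 2, share it too. At stake is whether a before-after difference may be reported as an established property of the lens.

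**Working it through.** **1. The plan's own figure.** No sample size is given for the within-ARM 2 tests. Table 9 sizes the between-arm CLUE test at 40 per arm (effect 9, margin -5, SDs 25.21 and 18.12). SE = √((25.21² + 18.12²)/40) = 4.909. The noncentrality is (9 + 5)/4.909 = 2.852. With Satterthwaite df 70.8 and critical value 1.994, power is 0.803. The 40 reproduces.

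**2. Aliasing.** Code intercept, lens and period for ARM 2. Every habitual-lens row is (1, 0, 0) and every AO1D row is (1, 1, 1). The matrix has three columns and rank 2. With lens effect λ and period effect π, the expected Visit 3 minus Visit 2 difference is λ + π, and ARM 2 alone cannot split it. Adding a period term leaves the model unidentified.

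**3. A shift created by step 2.5.** I simulated three scores per subject with no lens effect and no period effect, admitted those with Visit 1 ≥ 15, and kept those with Visit 2 ≥ 15. The underlying mean (12 to 20), SD (5 to 6) and reliability (0.6 to 0.8) are assumptions. Among all admitted subjects the mean Visit 3 minus Visit 2 difference was about 0. Among those kept it was an apparent improvement of about 0.2 points (mean 20, SD 5, reliability 0.8) to 1.9 points (mean 12, SD 6, reliability 0.6). The Per-Protocol set requires all visits, so it contains only the kept subjects.

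**4. What a shift does to the superiority rule.** Take λ = 0, 40 pairs, df 39 and a two-sided 95% interval. The SDs are the historical difference SDs in Tables 7 and 8; using them as within-subject SDs is an assumption, and so is every shift.

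| Endpoint | SE | Assumed shift | Shift/SE | P(false superiority) |
|---|---|---|---|---|
| CLDEQ-8 | 7.17/√40 = 1.134 | 1 | 0.882 | 0.136 |
| | | 2 | 1.764 | 0.405 |
| | | 3 | 2.646 | 0.733 |
| CLUE | 25.21/√40 = 3.986 | 5 | 1.254 | 0.231 |
| | | 8 | 2.007 | 0.499 |

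With no shift the value is 0.025. With the ARM 2 SDs of Table 9 the values are higher: 0.234, 0.694 and 0.959 for CLDEQ-8 (SD 5.0), and 0.398 and 0.777 for CLUE (SD 18.12). The same probabilities apply to false non-inferiority when the true lens effect lies exactly at the margin.

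**5. The gate.** These rates are conditional on reaching the secondary tests. With no CLUE effect the primary passes with noncentrality 5/4.909 = 1.019, that is in about 17% of trials; at an effect of 9 it passes in about 80%. For CLUE with no lens effect, the joint rate of passing the primary and then falsely declaring within-arm superiority is about 4% to 7% for a shift of 5 and 8% to 13% for a shift of 8. This takes a subject's two successive changes to be correlated between 0 and -0.7 (assumed).

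**6. Can the trial estimate the period effect?** AO1D is worn in ARM 1 up to Visit 2 and in ARM 2 up to Visit 3. Using the AO1D 2-week SDs in Tables 7 and 8, the SE of that contrast is 6.35√(2/40) = 1.42 for CLDEQ-8 and 18.78√(2/40) = 4.20 for CLUE. The 95% half-widths are about 2.8 and 8.4 points, before any loss through step 2.5. In the simulation of item 3 the baseline-adjusted contrast on observed cases was biased by about 0.1 to 1.1 points, with ARM 2 looking worse. That is opposite in direction to the within-arm artefact.

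**The case against.** The strongest reply is that the plan already protects its main claims. The primary and the first secondary analysis compare ARM 1 with the first period of ARM 2. They are randomised and free of this aliasing, and Section 2.3 makes the primary decisive for the study objective. That stands, and it limits the point to the two within-ARM 2 secondary tests and what follows from them. It does not cure them: a randomised non-inferiority result on CLUE does not validate a separate before-after superiority statement. Deferring detail to a stand-alone SAP does not help either, since the decision rules are already written.

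Three stronger readings are tempting and not supported.

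- A reader might take the percentages above as the trial's error rates. They ignore the gate, and the documents give no size for any period shift.
- A reader might treat ARM 2 at Visit 3 against ARM 1 at Visit 2 as a clean randomised estimate of the period effect. Step 2.5 makes the ARM 2 side a subset selected on outcome after randomisation.
- A reader might list novelty of the lens as a period effect. ARM 1 also receives a new, over-labelled lens while ARM 2 keeps its open-label one, so novelty enters the between-arm comparison as well. It is a separate matter that this fix does not settle. Season is a weak candidate, with visits two weeks apart and enrolment spread over months.

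The regression artefact also has a limit. Removal under step 2.5 depends on a recorded score, so a likelihood model on ITT that keeps removed subjects' Visit 2 scores would reduce it. It would not remove a true period effect.

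**Conclusion.** The decision rules for the two within-ARM 2 secondary endpoints are wrong as written. The aliasing of lens and period follows from the design and needs no assumption. The regression artefact in Per-Protocol completers follows from step 2.5; its size, about 0.2 to 1.9 CLDEQ-8 points, rests on assumed score distributions. The false-superiority rates (14%, 41%, 73% for CLDEQ-8; 23%, 50% for CLUE) are illustrations that depend on assumed shifts, a zero lens effect and the primary having passed. The documents do not show that a period effect exists, and the primary conclusion is untouched. This should be corrected because it changes what may be claimed from the secondary results.

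**What to change.** In Section 14.6, for CLDEQ-8 total score and CLUE comfort within ARM 2, replace the language that declares non-inferiority and superiority established. State that these are supportive before-after comparisons estimating lens plus period. Apply the same wording to the within-ARM 2 tertiary items in Section 14.7. State that lens claims on CLUE and CLDEQ-8 come only from the ARM 1 versus ARM 2 comparisons at Visit 2, already planned as the primary and first secondary analyses. Drop the crossover label in step 1.16.

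Optionally, report AO1D in ARM 2 at Visit 3 against AO1D in ARM 1 at Visit 2 as a descriptive period check. Fit it by a likelihood model on all randomised subjects with ARM 2 Visit 2 scores included, not on completers, and do not call it a clean randomised estimate. With half-widths of at least about 2.8 CLDEQ-8 and 8.4 CLUE points, it cannot rule out a relevant shift, so the wording change has to carry the correction.

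This needs no new data, visits or subjects. The cost is that the within-arm superiority statement is lost.
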